6. State inclusion criteria for enrollment in study:

Inclusion Criteria include: 1. Age 18 years or older, 2. Discharge from inpatient unit for suicidal ideation or attempts, or placement on the high-risk suicide list maintained by suicide prevention coordinators, or patient from outpatient service that meets criteria of 4 or 5 on CSSRS or attempt within the past year 3. Concurrence from the patient's mental health provider for the Veteran to participate in the study and the provider is willing to work with the research team.

7. State exclusion criteria for enrollment in study:

Exclusion Criteria include: 1. Unable to provide informed consent or complete study requirements, 2. Unable to speak English, 3. Cognitive difficulties that impair consent Capacity, 4. Unable or unwilling to provide at least one verifiable contact for emergency or tracking purposes, 5. Unable to attend outpatient group treatment program or tolerate group therapy format, 6. Active alcohol or opiate dependence requiring medically supervised withdrawal, 7. Schizophrenia diagnosis, 8. Participation in another intervention RCT.

8. Will vulnerable subjects be enrolled in this study?

YES	X	NO	
------------	----------	-----------	--

	YES	NO
Individuals with lack of decision-making mental capacity		X
Economically/socially disadvantaged persons	X	
Educationally disadvantaged persons	X	
Pregnant women, for minimal risk only		

Fetuses Requires Medical Center Director authorization. See IRB SOP.

Children Requires Medical Center Director authorization. See IRB SOP.

Prisoners Requires CRADO authorization. See IRB SOP.

If Yes for any answer, provide a means by which vulnerability is determined: **Vulnerability will be determined through gathering basic demographic data of each participant. James J. Peters VA Medical has a population of veterans who are economically, socially, and educationally disadvantaged; thus, the PI anticipates recruiting from vulnerable populations.**

9. Are prospective subjects likely to feel vulnerable to coercion or undue influence to enter the study?

YES		NO	X
-----	--	----	---

a. Are there any payments to subjects?

YES	X	NO	
-----	---	----	--

b. If No, proceed to question 9.c.

How much are the payments? **\$50-\$75**

Provide a schedule (timing) of payments. **Baseline, post intervention, 3 months post completion of intervention, 6 months post completion of intervention**

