As mentioned above, upon hearing the description of the study, the participant will be required to describe the procedures to the person obtaining consent, summarize what is expected of him or her and list two risks involved. This will ensure that participants understand the implications of their decision to participate and are able to make a well-informed decision and communicate this decision to the person obtaining consent. Consent will be obtained in a private setting by an investigator to minimize any power differential that the participant might feel. Participants unable to communicate with the investigator for any reason will not be included in the study. Only subjects having the capacity to give informed consent will be enrolled in the study. The recruitment process will not be coercive or unduly influencing, as participants enter the research study voluntarily and understand that they have the right to withdraw at any time. Subjects will be told that non-participation in the study will not affect any current treatments they are receiving at VA or elsewhere.

13. Summarize what actually will be done to the subjects during their participation in the study:

The subject will fill out the informed consent. They will then fill out a series of clinician interviews and self-report measures asking questions related to thoughts and feelings about suicide, general mental and physical health, and relationship with other. After these are completed half the group will be randomized to the PLF intervention arm in which Veterans will participate in the 10 weekly groups.

a. Provide a clear description of what is being done for research purposes and what is being done as part of "usual care":

For research purposes: Initial consult with research investigators and consenting, which will take approximately 30 – 45 minutes, completing assessments (1.5 hours) and answering interview-style questions pertaining to the research topic (30 minutes).

Subject matter of the interview includes: communication quality with others, overall life satisfaction, frequency of suicidal ideation or urges, and reasons for attempting suicide.

“Usual care”: Subjects will be able to continue all regular treatment outside of the study.

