b. Provide a detailed **list of tests and procedures** that will be performed for research purposes (e.g., blood tests, urine tests, cultures, interviews, questionnaires, surgical procedures, cardiac catheterization, pulmonary function tests, X-rays, scans, etc) during the course of the study. **List must indicate tests and procedures only for subjects who sign a VA consent form, regardless of where tests and procedures take place:**

Test /Procedure:	Where:	Performed by Whom: (Insert Name or TBD if not yet known)	When:	# of times:
Columbia Suicide Severity Rating Scale (CSSRS)– current & since last visit version	Research office	[name], [name]	0, 3, 6,12, weekly for PLF group participants	4
Access to Lethal Means	Research office	[name], [name]	0, 3, 6,12	4
Beck Depression Scale	Research office	[name], [name]	0, 3, 6,12	4
Beck Hopelessness Scale	Research office	[name], [name]	0, 3, 6,12	4
Self-report log based on the Modified Cornell Services Index (MCSI)	Research office	[name], [name]	0, 3, 6,12	4
Brief Survey of Safety Plan Utilization (BSSPU)	Research office	[name], [name]	0, 3, 6,12	4
Suicide-Related Coping Measure (SRCM)	Research office	[name], [name]	0, 3, 6,12	4
Group Psychotherapy Process Measure*	Research office	[name]	1,5,10 (weeks)	3

PLF treatment arm only		[name]		
Buss-Perry Aggression Questionnaire	Research office	[name], [name]	0, 3, 6,12	4
Reasons for Living	Research office	[name], [name]	0, 3, 6,12	4
Attitudes Towards Seeking Professional Psychological Help	Research office	[name], [name]	0, 3, 6,12	4
Insomnia Severity Index	Research office	[name], [name]	0, 3, 6,12	4
Beck Lethality Scale	Research office	[name], [name]	0, 3, 6,12	4
The Self-Injurious Thoughts and Behaviors Interview	Research office	[name], [name]	0, 3, 6,12	4
Suicide Intent Scale	Research office	[name], [name]	0, 3, 6,12	4
Beck Scale for Suicidal Ideation	Research office	[name], [name]	0, 3, 6,12	4
Barratt Impulsiveness Scale	Research office	[name], [name]	0, 3, 6,12	4

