Title: **Group ("Project Life Force") vs. Individual Suicide Safety Planning RCT**

NCT Number: **NCT03653637**

Date: **05/12/2025**

Primary Statistical Analysis Plan

The primary outcome of suicidal behavior will be analyzed using a Cox Proportional Hazard Regression, with treatment condition (PLF+TAU vs. TAU) and baseline suicidal behavior level as predictors, and incidence and time to the first suicidal behavior during the study course as the outcome variables. The model will adjust for treatment site. Kaplan-Meier estimates of the cumulative hazard function for both groups will be graphed and the proportionality assumption checked. If the hazard functions are not proportional, the non-parametric log-rank test will be used instead, with treatment condition as predictor, and we will use a sensitivity analysis to test the effect of baseline suicidal behavior severity by splitting the treatment conditions by the presence/absence suicidal behavior.

Most secondary and other outcomes (depression, hopelessness, thwarted belongingness, aggression dimensions, insomnia and suicide-related coping) will be analyzed in Linear Mixed Effects (LME) regression models. All LMEs will be adjusted for site and will include randomization condition, time, and a randomization by time interaction. The treatment effect of PLF+TAU vs TAU will be the treatment by time interaction. Time will be treated as a linear variable. Mixed-effect models can be fit to data with dropout or missing values as long as the data is missing at random, thus, attrition does not necessarily reduce the number of participants included in these analyses.

For the two outcomes (drug and alcohol use) that are only measured at the one-year follow-up (with retrospective questions about the past 12 months), we will compare between PLF+TAU and TAU with t-tests or Mann-Whitney U tests where appropriate.

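### If hazards look non-proportional, the SAP's log-rank fallback drops the planned site and baseline adjustment without remedying non-proportionality; the effect is small and wording fixes it

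*SAP*

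**What the plan says.** The SAP's primary analysis is a Cox regression for time to first suicidal behavior, "with treatment condition (PLF+TAU vs. TAU) and baseline suicidal behavior level as predictors". It adds: "The model will adjust for treatment site". Then "Kaplan-Meier estimates of the cumulative hazard function for both groups will be graphed and the proportionality assumption checked". If the check fails: "If the hazard functions are not proportional, the non-parametric log-rank test will be used instead, with treatment condition as predictor". Baseline severity is then examined in a sensitivity analysis "by splitting the treatment conditions by the presence/absence suicidal behavior". Site is not mentioned again. The SAP gives no test or threshold for the check, no stratification or weighting for the log-rank, and no treatment contrast with an interval for that case.

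Protocol section 17.b sizes the survival comparison under exponential hazards in both arms, which are proportional. It mentions a weighted log-rank test only as the source of its variance inflation formula.

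Three protocol items bear on whether the fallback might be used and what it would lose:
- Item 13: "Veterans will participate in the 10 weekly groups".
- Table 13.b, C-SSRS schedule: "0, 3, 6,12, weekly for PLF group participants".
- Item 6, eligibility: "Discharge from inpatient unit for suicidal ideation or attempts", among other routes.

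**The concern.** The log-rank test is the score test of a Cox model with treatment as the only term. It needs no proportionality to be valid under the null. It is most powerful when hazards are proportional, though, and loses power alongside Cox when they are not. Replacing adjusted Cox with it therefore answers a failed check by deleting covariates.

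Three things are at stake:
- some power, if baseline behavior or site is prognostic;
- a named contrast with an interval, in the case where a single hazard ratio says least;
- certainty about which test is primary, because the switch has no stated criterion.

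Non-proportionality is foreseeable. Ten weekly sessions cover about 2.3 of 12 months (70 days / 30.4), and only PLF participants have weekly C-SSRS ratings, so both effect and ascertainment could differ early and late. Eligibility admits ideation without an attempt, so baseline behavior can vary between participants and may be prognostic.

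**Working it through.** **Inputs from protocol 17.b.** TAU event rate 49%; 35% reduction; 20% dropout; exponential hazards; N=145; m=5 and ICC 0.01. Item 13 gives 1:1 allocation.

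**Assumptions.** Two-sided 5%; 12 months of follow-up; the 35% read as a risk reduction (49% to 31.85%); baseline behavior present in half of participants with hazard ratio (HR) 1 to 3; four sites (from the four VA centers in 17.a, although 3.a, 4.e and 11 place enrollment at JJPVA), with no effect or a log-hazard spread of ±0.4. The documents give no prognostic strengths.

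**1. The plan's own figure.** HR = ln(1−0.3185)/ln(1−0.49) = 0.3835/0.6733 = 0.57, with log −0.563.
- Events for 80% power: 4(1.96+0.8416)²/0.563² = 31.40/0.317 = 99.04, so 100.
- N=145 without dropout gives 145 × (0.49+0.3185)/2 = 58.6 events. Dividing by an assumed inflation 1+(5−1)×0.01 = 1.04 gives 56.4, and power Φ(√(56.4/4)×0.563 − 1.96) = Φ(0.153), or 56%.
- With exponential dropout about 53 events remain: Φ(√(53/4)×0.563 − 1.96) = Φ(0.089), or 54%.

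So 80% is not reproduced for a total of 145. That is a separate matter. It matters here only because it explains why the simulated powers below sit in the low to mid 50s.

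**2. Does the switch help?** In simulated trials with proportional, late, early and crossing effects, plain log-rank and unadjusted Cox z-values correlated at 0.9994 or more. Late or early effects left the log-rank with about 19 to 25% power, and crossing hazards with about 7%. It offers no protection that Cox lacks.

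**3. What does dropping the adjustment cost?** Power (%) at N=145 if each test were always used:

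| Scenario | Adjusted Cox | Plain log-rank | Log-rank stratified by baseline |
|---|---|---|---|
| Proportional, baseline HR 1, no site effect (A) | 53 | 54 | 54 |
| Proportional, baseline HR 2, no site effect (A) | 54 | 52 | 54 |
| Proportional, baseline HR 3, no site effect (A) | 58 | 54 | 59 |
| Proportional, baseline HR 2, site ±0.4 (B) | 54.7 | 51.4 | 53.4 |
| Proportional, baseline HR 3, site ±0.4 (B) | 54.1 | 48.3 | 52.8 |
| Proportional, baseline HR 3, site also prognostic (C) | 57.8 | 51.0 | 56.4 |
| No effect to month 3, baseline HR 3, no site effect (A) | 26 | 25 | 26 |
| No effect to month 3, baseline HR 3, no site effect (B) | 25.2 | 22.0 | 25.0 |
| No effect after month 6, baseline HR 3, site ±0.4 (B) | 27.5 | 22.4 | 25.7 |

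Set A has 10,000 trials per cell, with the 12-month risks held at 49% and 31.85%. Set B has 2,000, with the conditional HR held at 0.569; its Monte Carlo error is √(0.25/2000) = 1.1 points at most. Set C is a third simulation.

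Under proportional hazards the plain log-rank gives up about 0 to 4 points when only baseline matters. Set C gives 54.5 − 50.8 = 3.7 at baseline HR 3; set B gives 54.0 − 48.6 = 5.4. With site prognostic as well at baseline HR 3, the loss is 54.1 − 48.3 = 5.8 or 57.8 − 51.0 = 6.8. Under a delayed effect it is 0 to 3. In the early-effect cell shown it is 27.5 − 22.4 = 5.1.

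**4. The whole rule.** The SAP gives no trigger, so assume a Schoenfeld-residual test at 5% or 20%. In set A the fallback fires in 5–6% or 20–22% of proportional trials, and in 15–16% or 36–38% of delayed-effect trials. Power of the whole rule is within 0.4 or 1.0 point of always using adjusted Cox. In set B (5% trigger, baseline HR 3, site ±0.4) it moves from 54.1 to 53.8 under proportionality and from 27.5 to 26.3 with the early effect. The cost is about 1 point.

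**5. Type I error.** Adjusted Cox, both log-rank tests and the fixed-trigger rule lie between 4.3% and 5.7%.

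**6. Does the choice of test matter?** Adjusted Cox and plain log-rank fall on opposite sides of 5% in 6, 9 and 14% of proportional trials at baseline HR 1, 2 and 3.

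**7. A contrast that needs no proportionality.** Hazards are 0.6733/12 = 0.0561 and 0.3835/12 = 0.0320 per month. The 12-month restricted means are 0.49/0.0561 = 8.73 and 0.3185/0.03196 = 9.97 months, a difference of 1.23 (0.64 if the effect starts at month 3).

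**The case against.** A pre-specified log-rank test is a defensible choice: it is valid under the null without proportional hazards, and the SAP nowhere claims that it restores power. Keeping Cox does not cure non-proportionality either; in the delayed-effect cells of set A both tests have about 25%. Both points stand. The case for change is only that the switch gives up planned adjustment for nothing.

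It is also fair that the SAP is not silent on description. Kaplan-Meier estimates are graphed and incidence is named as an outcome variable. A reader might infer that the fallback leaves no summary of the effect; what is missing is a named contrast with a confidence interval. A reader might also infer that the switch turns on eyeballing curves by arm. The SAP does not say that the check is visual, only that it is made; the fair complaint is the missing criterion.

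Finally, baseline presence/absence may vary little. Protocol 3.b describes Veterans with a history of ideation and attempts, while item 6 admits ideation alone. If nearly all have prior behavior, the assumed 50% split is too generous and the loss from omitting baseline shrinks. The documents do not settle this.

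**Conclusion.** The point holds as a minor one, for consideration. If the fallback is used, the primary test loses its site and baseline adjustment, and non-proportionality is no better handled. At N=145 under proportional hazards the loss is about 0 to 4 points when only baseline is prognostic (5.4 in the smaller set) and about 6 to 7 when site is too, at baseline HR 3. It is about 1 point over the whole rule. These test-against-test figures compare each test across all trials and serve as a guide to trials where the fallback is used. They depend on the assumed prognostic strengths, four sites and, for the whole rule, the assumed Schoenfeld trigger.

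The stronger inference, that the two-step rule inflates type I error, is not supported. Size stays near 5% for any fixed trigger. It reaches 6.4 to 7.2% at N=145 only if whichever test is significant is reported, which the SAP does not permit. The practical reasons to act are the unstated criterion, given how often the two tests disagree, and the missing contrast.

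**What to change.** In the SAP, state that the primary test is the treatment coefficient in the Cox model adjusted for site and baseline suicidal behavior, whatever the proportionality check shows. Add that, if hazards appear non-proportional, the 12-month restricted mean difference (or the difference in 12-month event probability) will also be reported with a confidence interval. This does not restore power under non-proportionality.

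If the log-rank fallback is kept, stratify it by presence/absence of baseline suicidal behavior with a stated lookback window, and by site where strata are large enough. State the test and threshold that trigger it.

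The change is wording only; both covariates are already in the planned model. Against the plain log-rank it costs at most about 1 point of power if neither baseline nor site is prognostic, or up to about 3 points at N=145 if the log-rank is stratified by baseline and site jointly.

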All data will be de-identified before it is entered into a redcap database at the JJPVA, Philadelphia VA, Northport VA, and Central Texas VA over the intranet. All principal analyses will be conducted based on the intention-to-treat principle. Linear mixed models will be used to examine changes in primary and secondary outcomes for Veterans over time and to examine whether the effects of PLF and TAU on these outcomes vary with time adjusted for the time-dependent treatment, covariates of interest and imbalanced baseline prognostic factors, using data reduction methods as appropriate. *For the PLF subjects, individual's random effect will be nested within the group they are assigned to, while for TAU subjects, they will be nested within the clinician effect.* All data will be entered into an SPSS database at the JJPVA constructed by the data manager. Tenets of our data system include double data entry, range checks and exclusion of identifiers that can be directly traced to individuals. Preliminary analyses will include computing descriptive statistics and inspecting features and patterns of data to determine whether data transformations are needed. Quantitative measures will be graphed and their distribution inspected for any outlier value, which will be winsorized. All principal analyses will be conducted based on the intent-to-treat principle, that is, all Veterans with data will be included, regardless of the actual treatment received. For subjects who drop out during the study, their data up to that point will be used, but not carried forward to subsequent time points. We will also conduct an economic cost analysis of the Project Life Force intervention to compare cost effectiveness of telehealth groups versus the in-person groups pre-COVID. We will use an implementation science framework, The Consolidated Framework for Implementation Research, to determine barriers and facilitators of the telehealth-delivered PLF safety planning intervention. Development of the script and qualitative analysis will be conducted by [name]; a qualitative and implementation expert.

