For the survival analysis comparing the PLF and TAU treatment conditions, we assumed a 20% dropout in both groups based on previous safety planning data to date using SAFE-VET, exponential hazard functions, and considered four scenarios of suicide behavior reduction of PLF over TAU. We assumed a base rate of 49% for SB in the TAU group based on published data from ED-SAFE. The sample sizes needed for 80% power were calculated using the “Proc Power” procedure from SAS software © 2002- 2012. In the absence of pilot data, we used a published formula for the Variance Inflation Factor from the weighted log-rank test, to adjust the required sample size for within-group, and within-clinician, dependence. We assumed m=5 subjects per group or clinician, and an ICC for suicidal behavior within the group of r=0.01 based on literature. While power analyses were calculated for several reduction rates, we selected the 35% reduction rate as the most reasonable estimation for the reasons outlined below. The composite suicide behavior outcome has minimal data outside of ED-SAFE’s reduction of 18% in non-veterans recruited from an emergency room. Stanley and Brown’s SAFEVET data on Veterans presenting to an ED, reported a 45% reduction in suicide attempts (however the composite definition of suicidal behavior was not used). Moreover we anticipate PLF to have increased potency over SAFEVET due to the group setting and greater number of in-person sessions. Balancing the enhanced potency of the PLF intervention with the new composite definition of SB, the 35% reduction scenario is reasonable. Therefore, we expect the reduction to be above the minimum values indicated, and are confident that N=145 will provide ample power for this aim. Then, the research team included an additionally 35 to be consented who would likely not screen into the study or meet inclusion/exclusion criteria.

18. Community-based Participatory Research

Is this research based on Community-based participation?

YES		NO	X
------------	--	-----------	----------

If Yes, answer questions (a-h). If No, proceed to Question 19.

a. Describe the community that will be involved in this research:

b. What is the role of the community in this research?

c. Does this research include a community organization that is engaged in research?

YES		NO	
------------	--	-----------	--

If Yes, does that organization have a Federal Wide Assurance (FWA)?

YES		NO	
------------	--	-----------	--

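### The SAP names no therapy-group or clinician term, although the protocol nests participants in its mixed models and sizes the survival comparison for that dependence; at the plan's own ICC the effect is small

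*SAP*

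**What the plan says.** **Design.** Protocol section 13 describes a "PLF intervention arm in which Veterans will participate in the 10 weekly groups". The procedures table in 13.b lists ten weekly sessions, so this means ten weekly meetings and not ten separate groups.

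**Protocol analysis.** For the linear mixed models, section 17.a says that a PLF individual's "random effect will be nested within the group they are assigned to, while for TAU subjects, they will be nested within the clinician effect".

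**Protocol sample size.** Section 17.b applies a variance inflation factor to the survival comparison "to adjust the required sample size for within-group, and within-clinician, dependence". Its inputs are: "We assumed m=5 subjects per group or clinician, and an ICC for suicidal behavior within the group of r=0.01".

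**SAP (Primary Statistical Analysis Plan).**
- The Cox model is specified "with treatment condition (PLF+TAU vs. TAU) and baseline suicidal behavior level as predictors", with adjustment for site.
- If hazards are not proportional, "the non-parametric log-rank test will be used instead, with treatment condition as predictor".
- For the mixed models, "All LMEs will be adjusted for site and will include randomization condition, time, and a randomization by time interaction"; no random effect is named.
- Drug and alcohol use at 12 months are compared by t-tests or Mann-Whitney tests.

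No frailty, cluster-robust variance, therapy-group term or clinician term appears in the SAP. Site is the only grouping factor named.

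**The concern.** People treated in the same therapy group share sessions, a leader and each other, so their outcomes may be correlated. The sponsor thought this plausible enough to model in the protocol and to pay for in the sample size. Inflating the sample size protects power. It does not protect the type I error of a test that then ignores the dependence. If outcomes correlate within therapy groups, the standard errors of the Cox, log-rank and 12-month tests are too small and their confidence intervals too narrow.

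Site adjustment does not remove this, because several groups or clinicians can sit within one site. In the mixed models the gap is of another kind: with no random effects listed, their structure could be chosen after the data are seen.

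**Working it through.** **Inputs from the documents (Protocol 17.b).** Cluster size m = 5; ICC = 0.01, given for suicidal behavior only; dropout 20%; N = 145. The power statement gives no alpha, so I assume two-sided 0.05.

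**Inflation factor.** VIF = 1 + (m − 1) × ICC = 1 + 4 × 0.01 = 1.04. If only PLF is clustered and allocation is equal, the variance of the treatment contrast is inflated by (1.04 + 1)/2 = 1.02.

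**Type I error of a test that ignores clustering** = 2 × Φ(−1.96/√VIF).

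| ICC | Source | VIF, both arms | Type I, both arms | VIF, PLF only | Type I, PLF only |
|---|---|---|---|---|---|
| 0.01 | protocol | 1.04 | 5.5% | 1.02 | 5.2% |
| 0.05 | assumed | 1.20 | 7.4% | 1.10 | 6.2% |
| 0.10 | assumed | 1.40 | 9.8% | 1.20 | 7.4% |

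With both arms clustered at ICC 0.01, standard errors are understated by a factor of √1.04 = 1.020, and 145 participants carry the information of 145/1.04 = 139.4.

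**12-month outcomes after 20% dropout.** The effective cluster size falls to 1 + 4 × 0.8 = 4.2, so VIF = 1 + 3.2 × ICC. For ICC 0.01, 0.05 and 0.10, type I error is 5.4%, 6.9% and 8.8% (both arms) or 5.2%, 5.9% and 6.9% (PLF only).

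**Simulation check.** The settings were 20,000 null trials each, clusters of 5, 14 or 29 clusters per arm, a 49% event rate and 20% dropout, without the SAP's covariates.
- Naive Cox at ICC 0.01: 5.0–5.2% (PLF only) and 5.3% (both arms).
- Naive Cox at ICC 0.05: 5.8–6.2% and 6.9–7.4%. At 0.10: 7.1–7.4% and 9.5–9.7%.
- Clinicians shared equally across arms, with no therapy-group effect: 4.7–5.0%, 4.5–4.6% and 3.9–4.0% at the three ICCs. The naive test is then conservative.
- Cluster-robust Cox variance at ICC 0.01, both arms, with 14 and 29 clusters per arm: 6.6% and 5.6% with a normal reference, but 5.0% and 4.8% with a t reference on clusters minus 2 df.

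**Mixed models.** The SAP's treatment effect is the treatment-by-time interaction. A constant cluster intercept largely cancels from it, so only between-cluster variation in change over time matters. If 5% or 10% of slope variance lay between clusters (assumed), the naive slope test would run at 6.1–6.3% or 7.0–7.2% (PLF only) and 7.3–7.7% or 9.4–9.5% (both arms).

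**Interval width of a clustered primary analysis** = (t/1.96) × √VIF, at ICC 0.01. For PLF only, TAU participants are independent units, so the Satterthwaite df is (1.04 + 1)² / [1.04²/(k − 1) + 1/(n − 1)], with k PLF groups and n TAU participants.

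| N = 145 read as | Clustering | df | t | Width ratio |
|---|---|---|---|---|
| total (14–15 clusters per arm) | PLF only | 43–44 | 2.02 | 1.04 |
| total | both arms | 27 | 2.05 | 1.07 |
| per arm (29 clusters) | PLF only | 91 | 1.99 | 1.02 |
| per arm | both arms | 56 | 2.00 | 1.04 |

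**The case against.** **The effect is negligible at the only documented ICC.** This largely stands for the primary outcome. The Monte Carlo standard error at 20,000 runs is about 0.15 points, so the simulated PLF-only Cox values cannot be told apart from 5%. The larger error rates rest on ICCs and slope-variance shares that I assumed, and site and baseline suicidal behavior might absorb some of the between-cluster variation. But 0.01 is given for suicidal behavior alone, and nothing in the documents shows that it holds for depression, hopelessness, coping or substance use.

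**The direction is not settled.** This stands for clinicians. The SAP compares PLF+TAU with TAU, and Protocol 13.a says "Subjects will be able to continue all regular treatment outside of the study", so the same clinicians may treat both arms; the documents do not say. Sharing would make the naive tests conservative with respect to the clinician effect. The therapy-group part applies in any layout, since only PLF participants attend the groups.

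**The SAP is silent; it does not contradict the protocol.** This stands for the mixed models. A reader might infer that the SAP dropped the nesting, but it omits even the participant-level random effect that a mixed model needs, so its silence is not evidence of that. It does not rescue the other tests. The nesting sentence in 17.a covers linear mixed models only, so the Cox, log-rank and 12-month tests have no clustered version to inherit. For the same reason, the SAP's Cox model does not break any model term stated in the protocol.

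**Conclusion.** The point holds as a gap between protocol and SAP that is cheap to close. The SAP's time-to-event and 12-month tests, run as written, ignore a dependence that the protocol's own sample size assumes. The mixed models are under-specified, not shown to conflict with the protocol.

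For the primary outcome, type I error is about 5.2% (PLF only) to 5.5% (both arms clustered separately), given m = 5, ICC 0.01 and two-sided alpha 0.05. For the other outcomes the size is unknown: 6.2% to 9.8% before dropout across the assumed ICCs of 0.05 and 0.10.

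A reader might go further and infer that the primary test is materially invalid, or that a clustered primary Cox model is required. The documents support neither: the stated ICC moves the error rate by half a point at most, and the clinician part could go either way.

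**What to change.** In the SAP:

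1. Add a pre-specified clustered analysis of the primary outcome, at least as a sensitivity analysis, for therapy group in PLF and clinician in TAU. Use a shared frailty or a cluster-robust variance with a small-sample correction, and give a clustered version of the log-rank fallback. Do not use an uncorrected robust variance: at about 6.6% with 14 clusters per arm, it does worse than the naive test.
2. State the mixed-model random effects and carry over the partial nesting of Protocol 17.a. A group-level effect on change over time is worth considering, because that is where clustering would affect the interaction. It is optional, since it goes beyond the protocol.
3. Use a cluster-adjusted comparison for the 12-month drug and alcohol outcomes.
4. Report the estimated ICCs. A sentence on whether the same clinicians serve both arms would let a reader judge the direction of the clinician effect.

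**Cost.** SAP wording, plus group and clinician identifiers that the protocol's nested model already needs. As a sensitivity analysis, the primary interval is unchanged. As the primary analysis with a small-sample t correction, intervals widen by about 4% (PLF only) to 7% (both arms) if N = 145 is the total, or about 2% to 4% if it is per arm.
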